10.6.3.1. Male Participants With Partners Who Become Pregnant

- The Investigator will attempt to collect pregnancy information on any male participant's female partner who becomes pregnant while the male participant is in this study. This applies only to male participants who receive study drug.
- After obtaining the necessary signed informed consent from the pregnant female partner directly, the Investigator will record pregnancy information on the appropriate Pregnancy Outcome/Breastfeeding form and submit it to Alexion within 24 hours of learning of the partner's pregnancy. The female partner will also be followed to determine the outcome of the pregnancy. Information on the status of the mother and child will be forwarded to Alexion. Generally, the follow-up will be no longer than 3 months following the estimated delivery date. Any termination of the pregnancy will be reported regardless of fetal status (presence or absence of anomalies) or indication for the procedure.

10.6.3.2. Female Participants Who Become Pregnant

- The Investigator will collect pregnancy information on any female participant who becomes pregnant while participating in this study. The initial Information will be recorded on the appropriate form and submitted to Alexion within 24 hours of learning of a participant's pregnancy.
- The participant will be followed up to determine the outcome of the pregnancy. The Investigator will collect follow-up information on the participant and the neonate and the information will be forwarded to Alexion. Generally, follow-up will not be required for longer than 3 months beyond the estimated delivery date. Any termination of pregnancy will be reported, regardless of fetal status (presence or absence of anomalies) or indication for the procedure.
- While pregnancy itself is not considered to be an AE or SAE, any pregnancy complication or elective termination of a pregnancy for medical reasons will be reported as an AE or SAE. A spontaneous abortion (occurring at < 22 weeks gestational age) or still birth (occurring at > 22 weeks gestational age) is always considered to be an SAE and will be reported as such. Any post-study pregnancy related SAE considered reasonably related to the study drug by the Investigator will be reported to Alexion as described in Section 8.4.4. While the Investigator is not obligated to actively seek this information in former study participants, he or she may learn of an SAE through spontaneous reporting.
- Any female participant who becomes pregnant while participating in the study will discontinue study drug.

10.7. Handling of Human Biological Samples

All research and biological samples, including those for possible future research, are subject to national regulations and will only be conducted in a specified country if approved in that country.

Handling, storage, and shipment of biological samples are detailed in the laboratory manual.

10.7.1. Chain of Custody

A full chain of custody is maintained for all samples throughout their lifecycle.

The Investigator at each site keeps full traceability of collected biological samples from the participants while in storage at the site until shipment or disposal (where appropriate) and records relevant processing information related to the samples while at the site.

The sample receiver keeps full traceability of the samples while in storage and during use until used or disposed of or until further shipment and keeps record of receipt of arrival and onward shipment or disposal.

Alexion or delegated representatives will keep oversight of the entire life cycle through internal procedures, monitoring of study sites, auditing or process checks, and contractual requirements of external laboratory providers.

Samples retained for further use will be stored in the Alexion-assigned biobanks or other sample archive facilities and will be tracked by the appropriate Alexion team for the remainder of the sample life cycle.

All appropriately consented samples will be retained for a maximum of 25 years from study completion or other period as per local requirements.

10.7.2. Withdrawal of Informed Consent for Donated Biological Samples

If a participant withdraws consent to the use of donated biological samples, the samples will be disposed of/destroyed/repatriated, and the action documented. If samples are already analyzed, Alexion is not obliged to destroy the results of this research.

Following withdrawal of consent for biological samples, further study participation should be considered in relation to the withdrawal processes outlined in the informed consent.

The Investigator:

- Ensures the participant's withdrawal of informed consent to the use of donated samples is communicated immediately to Alexion or delegate.
- Ensures that relevant human biological samples from that participant, if stored at the study site, are immediately identified, disposed of as appropriate, and the action documented.
- Ensures that the participant and Alexion are informed about the sample disposal.

[figure not shown]
Alexion ensures the organization(s) holding the samples is/are informed about the withdrawn consent immediately and that samples are disposed of or repatriated as appropriate, the action is documented, and study site is notified.

10.8. Biomarkers

- Blood, urine, and kidney tissue samples will be collected for biomarker analyses and the data will be used for research (eg, exploratory) related to ravulizumab, or LN, IgAN, and related diseases. The samples may also be used to develop methods, assays, prognostics and/or companion diagnostics related to the study drug target, disease process, pathways associated with disease state, and/or mechanism of action of ravulizumab.
- The samples may be analyzed as part of a multistudy assessment of biomarkers in the response to ravulizumab to understand study disease or related conditions.
- The results of biomarker analyses may be reported in the CSR or in a separate study summary.
- Alexion or designee will store the samples obtained for biomarker analyses in a secure storage space with adequate measures to protect confidentiality.
- The samples will be retained while research on ravulizumab continues but no longer than 5 years after termination of the study or other period as per local requirements.

10.9. Systemic Lupus Erythematosus Diagnosis Classification Criteria

The 2019 European League Against Rheumatism / American College of Rheumatology Classification Criteria for SLE (Aringer, 2019) will be used for eligibility of the LN Cohort.

10.10. Revised 2018 International Society of Nephrology/Renal Pathology Society (ISN/RPS) Classification

Category	Recommendation
Class II	Definition for mesangial hypercellularity adjusted: Four or more nuclei fully surrounded by matrix in the mesangial area not including the hilar region
Class III and IV	
The term endocapillary proliferation is replaced by endocapillary hypercellularity
 
The term crescent is used for a lesion consisting of extracapillary hypercellularity, composed of a variable mixture of cells. Fibrin and fibrous matrix may be present; 10% or more of the circumference of Bowman's capsule should be involved.
 
Cellular crescent: more than 75% cells and fibrin and less than 25% fibrous matrix
 
Fibrous crescent: more than 75% fibrous matrix and less than 25% cells and fibrin
 
Fibrocellular crescent: 25% to 75% cells and fibrin and the remainder fibrous matrix
 
Adhesion: an area of isolated continuity of extracellular matrix material between the tuft and capsule even when the underlying segment does not have overt sclerosis
 
Fibrinoid necrosis: fibrin associated with glomerular basement membrane disruption and/or lysis of the mesangial matrix; this lesion does not require the presence of karyorrhexis
 
Elimination of segmental and global subdivisions of Class IV
 
Modification of the NIH lupus nephritis activity and chronicity scoring system to be used instead of the currently used A, C, and A/C parameters

Tubulointerstitial lesions	Indicate whether interstitial inflammation occurs in presence or absence of interstitial fibrosis

Source: [Bajema, 2018](#)

10.11. IgAN Diagnosis Classification Criteria

2016 Oxford Classification from the IgA Nephropathy Classification Working Group

Detailed description of the features present on:

- Light microscopy
- Immunohistochemistry or immunofluorescence
- Electron microscopy

Summary of 5 key pathologic features

- Mesangial score < 0.5 (M0) or > 0.5 (M1)
- Endocapillary hypercellularity absent (E0) or present (E1)
- Segmental glomerulosclerosis absent (S0) or present (S1); presence or absence of podocyte hypertrophy/tip lesions in biopsy specimens with S1
- Tubular atrophy/interstitial fibrosis #25% (T0), 26% to 50% (T1), or > 50% (T2)
- Cellular/fibrocellular crescents absent (C0), present in at least 1 glomerulus (C1), in > 25% of glomeruli (C2)

Quantitative data

- Total number of glomeruli
- Number of glomeruli with endocapillary hypercellularity, necrosis, extracapillary hypercellularity (cellular/fibrocellular crescents), global glomerulosclerosis, and segmental glomerulosclerosis

Source: [Trimarchi, 2017](#)

10.12. Systemic Lupus Erythematosus Disease Activity Index SELENA Modification (SLEDAI-2K)

The SLEDAI-2K is used to define Extrarenal SLE Flare defined by ≥ 4 points that is not accounted for by proteinuria, hematuria, urinary casts, hypocomplementemia, pyuria, or an increase in anti-dsDNA antibody level (ie, the shaded sections below).

Physicians Global Assessment:

0	1	2	3
None	Mild	Med	Severe
SLEDAI SCORE			

Check box: If descriptor is present at the time of visit or in the proceeding 30 days

Wt	Present	Descriptor	Definition
8		Seizure	Recent onset. Exclude metabolic, infectious or drug cause
8		Psychosis	Altered ability to function in normal activity due to severe disturbance in the perception of reality. Include hallucinations, incoherence, marked loose associations, impoverished thought content, marked illogical thinking, bizarre, disorganized, or catatonic behavior. Excluded uremia and drug causes.
8		Organic Brain Syndrome	Altered mental function with impaired orientation, memory or other intelligent function, with rapid onset fluctuating clinical features. Include clouding of consciousness with reduced capacity to focus, and inability to sustain attention to environment, plus at least two of the following: perceptual disturbance, incoherent speech, insomnia or daytime drowsiness, or increased or decreased psychomotor activity. Exclude metabolic, infectious or drug causes.
8		Visual Disturbance	Retinal changes of SLE. Include cytoid bodies, retinal hemorrhages, serious exudate or hemorrhages in the choroids, or optic neuritis. Exclude hypertension, infection, or drug causes.
8		Cranial Nerve Disorder	New onset of sensory or motor neuropathy involving cranial nerves.
8		Lupus Headache	Severe persistent headache: may be migrainous, but must be nonresponsive to narcotic analgesia.
8		CVA	New onset of cerebrovascular accident(s). Exclude arteriosclerosis
8		Vasculitis	Ulceration, gangrene, tender finger nodules, periungual, infarction, splinter hemorrhages, or biopsy or angiogram proof of vasculitis
4		Arthritis	More than 2 joints with pain and signs of inflammation (ie, tenderness, swelling, or effusion).
4		Myositis	Proximal muscle aching/weakness, associated with elevated creatine phosphokinase/aldolase or electromyogram changes or a biopsy showing myositis.
4		Urinary Casts	Heme-granular or red blood cell casts
4		Hematuria	> 5 red blood cells/high power field. Exclude stone, infection or other cause.

Wt	Present	Descriptor	Definition
4		Proteinuria	> 0.5 gm/24 hours. New onset or recent increase of more than 0.5 gm/24 hours.
4		Pyuria	> 5 white blood cells/high power field. Exclude infection.
2		New Rash	New onset or recurrence of inflammatory type rash
2		Alopecia	New onset or recurrence of abnormal, patchy or diffuse loss of hair.
2		Mucosal Ulcers	New onset or recurrence of oral or nasal ulcerations
2		Pleurisy	Pleuritic chest pain with pleural rub or effusion, or pleural thickening
2		Pericarditis	Pericardial pain with at least 1 of the following: rub, effusion, or electrocardiogram confirmation.
2		Low Complement	Decrease in CH50, C3, or C4 below the lower limit of normal for testing laboratory.
2		Increased DNA binding	> 25% binding by Farr assay or above normal range for testing laboratory.
1		Fever	> 38°C. Exclude infectious cause
1		Thrombocytopenia	< 100,000 platelets/mm ³
1		Leukopenia	< 3000 White blood cell/mm ³ . Exclude drug causes.

_____ TOTAL SCORE (Sum of weights next to descriptors marked present)

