24-hr urine collection ^e	X											X	X ^f	One collection is needed as soon as possible during Screening. Two collections must be obtained within 2 weeks prior to Week 26 (Section 8.2.1)
Morning spot urine sample ^e	X	X	X	X	X	X	X	X	X ^g	X	X	X		Obtain sample prior to dosing, vaccination, and biopsy
eGFR	X	X	X	X	X	X	X	X	X	X	X	X ^f		One additional blood draw for eGFR (serum creatinine) is required within 2 weeks prior to the Week 26 visit.
Monitor for Renal and Extrarenal SLE Flare ^f		Continuous monitoring										X		Refer to Section 3.2.1 and 3.2.2 for definitions. Document use of additional standard of care therapy and/or repeat biopsy ^f , if applicable.
Blood sample for C3, C4, and CH50	X	X		X			X		X		X	X		
Safety Assessments														
Physical examination	X	X										X		
Abbreviated PE			X	X	X	X	X	X	X	X	X			
Vital signs ^h	X	X	X	X	X	X	X	X	X	X	X			

Table 1: Schedule of Activities During the Initial Evaluation Period: Screening to Week 26 Visit (LN Cohort)

Period	Screening	Initial Evaluation Period											Eval. for Renal Flare and Extrarenal SLE Flare	Notes
Visit	1	2	3	4	5	6	7	8	9	10	11			
Week	Up to 6 W		W1 ^a	W2	W4	W6 ^b	W10	W14	W18	W22	W26/ED ^c			
Days and Window	D -42 to -1	D1	D8 ± 2	D15 ± 3	D29 ± 3	D43 ± 5	D71 ± 5	D99 ± 5	D127 ± 5	D155 ± 5	D183 ± 5			
ECG ⁱ	X											X		
Prior medications and procedures	X													
Concomitant medications, nonpharmacologic therapies, and procedures		Continuous monitoring											X	
Adverse events	Continuous monitoring											X		
Clinical chemistry	X	X	X	X	X	X	X	X	X	X	X	X		
Hematology and coagulation	X	X	X	X	X	X	X	X	X	X	X			
Urinalysis and sediment	X	X	X	X	X	X	X	X	X	X	X	X	Obtain sample from a morning void prior to dosing	
Participant safety card review		X	X	X	X	X	X	X	X	X	X	X	Confirm participants carry safety card at all times	
Pharmacokinetic and Pharmacodynamic Assessments														
Blood samples for PK/PD ^j		B/P	X	T/P	X		T/P		T/P		T	X	Samples can be obtained anytime at ED Visit	
Blood samples for ADA		B			X		T				T		Samples can be obtained anytime at ED Visit	
Exploratory Assessments														
EQ-5D-5L		X					X				X			
SF-36		X					X				X			
FACIT-Fatigue		X									X			

Table 1: Schedule of Activities During the Initial Evaluation Period: Screening to Week 26 Visit (LN Cohort)

Period	Screening	Initial Evaluation Period										Eval. for Renal Flare and Extrarenal SLE Flare	Notes	
Visit	1	2	3	4	5	6	7	8	9	10	11			
Week	Up to 6 W		W1 ^a	W2	W4	W6 ^b	W10	W14	W18	W22	W26/ED ^c			

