Days and Window	D -42 to -1	D1	D8 ± 2	D15 ± 3	D29 ± 3	D43 ± 5	D71 ± 5	D99 ± 5	D127 ± 5	D155 ± 5	D183 ± 5			
SLEDAI-2K		X										X	X	Perform as needed for evaluation of Extrarenal SLE Flare
Blood and urine samples for biomarkers	X	X		X			X		X			X	X	
Blood sample for anti-dsDNA and anti-C1q	X	B										X	X	
Blood and urine samples for RTCA	X	X		X			X		X			X		To be performed at selected sites only. See Section 8.9.3
Kidney biopsy ^k												X ^k		Send local pathology report and microscopy slides to the Central Pathology Laboratory (Section 8.1.5.3)
Administration of Study Intervention														
Randomization		X												
Allowed concomitant LN therapy	X	Continuous monitoring											Section 6.5.1	
Ravulizumab or placebo		X	X	X		X		X		-- ^l			Administer after all other required tests/procedures	

Note: All assessments should be performed prior to administration of study drug on dosing days, unless otherwise specified.

^a The Week 1 Visit is not required for participants enrolled after completion of the Dose Confirmation Analysis (Section 9.5.1).

^b Visit can be conducted at the discretion of the Investigator.

^c For participants who discontinue the study prior to the end of the Initial Evaluation Period, the ED Visit should be completed as soon as possible. In addition, a Follow-up Phone Call must be performed 8 weeks following the participant's last dose of study drug to collect information on concomitant medications, nonpharmacologic therapies and procedures, and AEs.

Table 1: Schedule of Activities During the Initial Evaluation Period: Screening to Week 26 Visit (LN Cohort)

^d Weight should be obtained at every visit and measured predose on dosing visits. The dose regimen is based on the last recorded study visit body weight. If the study drug is prepared the night before a visit, the weight from the most recent study visit should be used.

^e The 24-hr urine collection and spot urine samples must be obtained prior to or > 7 days after biopsy procedures.

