Table 3: Schedule of Activities During the Extension Period: Week 26 Dose Administration, Week 34 to Week 50 Visits (LN Cohort)

Period	Extension Period				Eval. for Renal Flare and Extrarenal SLE Flare and Suboptimal Response	Notes Additional visits can be performed as needed. An ED Visit should be performed if participants discontinue early.
Visit	11	12	13	14		
Week	W26	W34	W42	W50/ED ^a		
Days and Window	D183	D239 ± 7	D295 ± 7	D351 ± 7		
Adverse events	Continuous monitoring				X	
Clinical chemistry		X	X	X	X	
Hematology and coagulation		X	X	X		
Urinalysis and sediment		X	X	X		Obtain sample from a morning void prior to dosing
Participant safety card review		X	X	X	X	Confirm participants carry safety card at all times
Pharmacokinetic and Pharmacodynamic Assessments						
Blood samples for PK/PD		T/P	T/P	X		Collect samples at any time during the Week 50/ED Visit
Blood samples for ADA		T	T	X		Collect samples at any time during the Week 50/ED Visit
Exploratory Assessments						
SF-36				X		
EQ-5D-5L				X		
FACIT-Fatigue				X		
SLEDAI-2K				X	X	Perform as needed for evaluation of Extrarenal SLE Flare
Blood samples for anti-dsDNA and anti-C1q				X	X	
Blood and urine samples for biomarkers		X	X	X	X	
Optional kidney biopsy ^f				X ^g	X ^f	Send the local pathology report and microscopy slides to the Central Pathology Laboratory (Section 8.1.5.3)
Administration of Study Intervention						
Allowed concomitant LN therapy	Continuous monitoring				X	Section 6.5.1
Ravulizumab or placebo	X	X	X			Administer after all other required tests/procedures

Table 3: Schedule of Activities During the Extension Period: Week 26 Dose Administration, Week 34 to Week 50 Visits (LN Cohort)

Note: During the Extension Period, participants in the LN cohort will continue to receive their randomized allocation of study drug (ravulizumab or placebo).

^a For participants who discontinue the study prior to the end of the Extension Period, the ED Visit should be completed as soon as possible. In addition, a Follow-up Phone Call will be performed 8 weeks following the participant's last dose of study drug to collect concomitant medications, nonpharmacological therapies and procedures, and AEs.

^b Weight should be obtained at every visit and measured predose on dosing visits. The dose regimen is based on the last recorded study visit body weight. If the study drug is prepared the night before a visit, the weight from the most recent study visit should be used.

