8.3.5. Clinical Safety Laboratory Assessments

- All protocol-required laboratory assessments, as defined in Section 10.2, must be conducted in accordance with the laboratory manual and the SoA (Section 1.3).
- The Investigator must review the laboratory report, document this review, and record any clinically relevant changes occurring during the study in the AE section of the CRF. The laboratory reports must be filed with the source documents. Clinically significant abnormal laboratory findings are those which are not associated with the underlying disease, unless judged by the Investigator to be more severe than expected for the participant's condition.
- All laboratory tests with values considered clinically significantly abnormal during participation in the study or within 8 weeks after the last dose of study drug should be repeated until the values return to normal or baseline or are no longer considered clinically significant by the Investigator or Medical Monitor.
 - If such values do not return to normal/baseline within a period of time judged reasonable by the Investigator, the etiology should be identified, and Alexion notified.
 - If laboratory values from non-protocol specified laboratory assessments performed at the institution's local laboratory require a change in participant management or are considered clinically significant by the Investigator (eg, SAE or AE or dose modification), then the results must be recorded in the CRF.

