8.9.2. SLEDAI-2K (LN Cohort Only)

The SLEDAI-2K tool (Section 10.12) assesses disease activity across 24 disease descriptors. The total score ranges from 0 to 105, with higher scores representing more significant degrees of disease activity.

The 18 disease descriptors of the SLEDAI-2K assessment will be used for the determination of Extrarenal SLE Flare (Section 3.2.2). Extrarenal SLE Flare is defined as an increase in SLEDAI-2K ≥ 4 points that is not accounted for by the disease descriptors of proteinuria, hematuria, urinary casts, hypocomplementemia, pyuria, or an increase in anti-dsDNA antibody level. Each disease descriptor is evaluated if present at the time of the visit or within the preceding 30 days.

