24-h urine	
• Total protein, total creatinine, total albumin, total sodium, creatinine clearance, and protein to creatinine ratio, albumin to creatinine ratio.
Spot urine studies	
• Protein, albumin, creatinine, and protein to creatinine and albumin/creatinine ratio
Routine urinalysis and urine sediment	
• Albumin• Bilirubin• Blood• Erythrocytes• Glucose• Ketones• Leukocyte esterase

Table 13: Protocol-Required Laboratory Assessments

Laboratory Assessments	Parameters
	
 • Nitrite • pH • Protein • Specific gravity • Urobilinogen • Urine sediment: number of RBCs/high-power field and number of RBC casts^b
PK/PD and immunogenicity	
 • Serum PK • Serum PD (free and total C5) • Immunogenicity (ADA)
Other study-specific tests	
 • HCV PCR viral load, HBV antigen and serology panel • HIV-1 and HIV-2 antibody • Serum follicle-stimulating hormone (as needed in women of nonchildbearing potential only) • Serum or urine human chorionic gonadotropin pregnancy test (as needed for WOCBPs)^a • Complement: C3, C4, and CH50 • Autoantibody profile: ANA, anti-dsDNA, anti-Sm, anti-RNP, anti-Ro, anti-La, anti-C1q, anti-phospholipid antibodies (LN cohort only)
	
 • Anti-ds-DNA antibody: to be measured by ELISA at all visits as part of SLEDAI Assessment (LN cohort only)

^a Serum pregnancy test at Screening and End of Study Visit/Early Discontinuation Visit, and local urine pregnancy test at all other times as specified in Schedule of Assessments.

^b For participants in the IgAN cohort, eligibility for hematuria can be determined via the local laboratory.

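### LN cohort: blinded sites may score SLEDAI-2K Low Complement from CH50 alone, and no masking rule names CH50, a readout that could suggest the treatment arm

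*Protocol*

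**What the plan says.** Protocol 10.12 gives the Low Complement item a weight of 2 and defines it as a "Decrease in CH50, C3, or C4 below the lower limit of normal for testing laboratory". The three tests are joined by *or*, so any one of them is sufficient.

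The schedules for the LN cohort (Protocol 1.3, Tables 1 and 3) each carry a row "Blood sample for C3, C4, and CH50", placed under efficacy assessments. Both tables mark that row in the flare-evaluation column. SLEDAI-2K is marked in the same column, with the instruction "Perform as needed for evaluation of Extrarenal SLE Flare".

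Protocol 6.3.2 keeps LN participants and site staff blinded through the Extension Period. It adds a general statement that Investigators receive only blinded information unless safety requires otherwise, and it names no laboratory test. Specific masking rules appear in three places:
- 8.7, for study drug concentration results
- 8.9.3, for RTCA results
- the schedule footnotes, for complement immunohistochemistry on biopsy, with the stated reason that it might unblind

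**The concern.** The protocol recognises that complement readouts can reveal treatment, and it closes that route for RTCA and for biopsy staining. CH50 is also a complement readout, measuring hemolytic activity, and no rule names it. Instead, 10.12 invites a blinded scorer to use it.

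Several LN outcomes depend on Investigator judgment. The most exposed is the extrarenal flare. Under 3.2.2, a qualifying flare becomes Severe only if the Investigator gives additional standard of care therapy. That choice makes the participant a Treatment Failure (3.2.4) and rules out CRR and PRR (3.2.5). If it happens before Week 26, it also triggers the carry-forward of the flare-time proteinuria value into the primary analysis (SAP 5.3.2). An Investigator who suspected the arm could lean one way or the other without intending to.

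**Working it through.** No plan figure needs reproducing here. The check is a count of draws and a comparison of texts.

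**Draws after the first dose (LN).** Day 1 is excluded because of the Table 1 note: "All assessments should be performed prior to administration of study drug on dosing days, unless otherwise specified".
- Table 1: Weeks 2, 10, 18, 26 = 4
- Table 3: Weeks 34, 42, 50 = 3
- Total: 4 + 3 = 7, of which Weeks 2, 10 and 18 (3 draws) precede the Week 26 visit
- Flare evaluations add unscheduled draws

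**Timing against dosing.** Maintenance doses fall on Day 15 and every 56 days after: 15, 71, 127, 183, 239, 295. Six of the seven draws are therefore predose on dosing days, and Week 50 (Day 351) is not a dosing day. Predose timing does not remove the signal, because Protocol 4.3 aims to hold complete inhibition to the end of the dosing interval.

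**When the form is completed.** After Day 1, SLEDAI-2K is scheduled at Weeks 26 and 50 only (2 of the 7 visits), plus flare evaluations. The count of seven refers to draws, not to scorings. The flare evaluation matters most, because CH50 and the form are scheduled together just when a treatment decision is pending.

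**Would CH50 be informative?** Protocol 2.1 says that ravulizumab binds C5 and blocks its activation, and 4.3 targets complete terminal inhibition. C3 and C4 lie outside that blockade. A low CH50 beside normal C3 and C4 is thus the pattern one would look for. This is inferred from mechanism: the documents give no CH50 values and do not state that the drug lowers CH50. Protocol 2.2.1 links low C3 and C4 with active LN, so low complement by itself does not identify the arm.

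**Texts side by side.** If the general sentence in 6.3.2 covers CH50, the site cannot score 10.12 as written. If the site scores 10.12 as written, it sees a pharmacodynamic result. No passage resolves this. It resolves in practice if CH50 is withheld and the row is scored from C3 and C4.

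**Reach into the score.** Hypocomplementemia is excluded from the Extrarenal SLE Flare definition (3.2.2, 8.9.2, 10.12), so the 2 points cannot create a flare.

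**The case against.** The strongest reply is that silence is not release. The general sentence in 6.3.2 can be read to cover CH50. Section 8.3.5 says that required tests "must be conducted in accordance with the laboratory manual and the SoA", and that manual may already withhold the result. Because the row can be scored from C3 or C4, 10.12 does not force disclosure. All of this stands, and it limits the point to a possible exposure.

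A reader might go further and infer from 8.3.5 that sites must see CH50, since "The Investigator must review the laboratory report, document this review" and Table 13 lists "Complement: C3, C4, and CH50". The documents do not support that:
- Section 10.2 speaks of review of the laboratory safety report.
- The schedules place CH50 under efficacy.
- Table 13 also lists serum PK, and 8.7 withholds concentration results, so the report in 8.3.5 cannot mean everything in Table 13.

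A reader might also infer a biased primary result. The primary measurement is 24-hour proteinuria from a central laboratory, and the documents give no inputs for an effect on the geometric mean ratio or type I error.

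The discretion is bounded too. Renal Flare and Suboptimal Response also need measured criteria, and 6.6 asks that additional therapy be discussed with the Medical Monitor. The Week 50 draw comes too late to influence much. What survives is narrow: the form as written uses a readout that could suggest the arm, and nothing in the protocol names it as masked.

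**Conclusion.** The gap is real, and closing it is a cheap improvement rather than the repair of a demonstrated flaw. Its extent is seven scheduled CH50 draws after the first dose, three of them before Week 26, plus draws at flare evaluations beside SLEDAI-2K, all within the period of LN site blinding.

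The consequence is a possible, undemonstrated influence on Investigator-judged decisions, mainly whether an extrarenal flare is treated and so counts as Severe and as Treatment Failure. The treatment-policy analysis in SAP 5.3.4 is a partial check on the carry-forward into the primary analysis, but it does not address CRR or PRR.

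The conclusion rests on two assumptions: that C5 blockade lowers CH50 visibly, which is inferred, and that the laboratory manual does not already withhold it, which is unknown. If the manual does, only a cross-reference is missing.

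**What to change.** 1. In Protocol 6.3.2 or 8.7, add: *In the LN cohort, CH50 results obtained after Day 1, from the central or a local laboratory, will not be reported to investigative sites or blinded sponsor personnel through Week 50.* If the laboratory manual already provides this, cite it instead. Local testing needs to be named because 10.2 requires local results when central results are late for response evaluation.
2. In 10.12, note that Low Complement is scored from C3 and C4 only after Day 1.

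The cost is one sentence or citation, one scoring note and a laboratory report setting. The downside is that an isolated low CH50 no longer adds 2 points to the post-baseline SLEDAI-2K total. No planned SAP analysis uses those points: the trajectory in SAP 5.4.9 leaves out the renal descriptors, among which that section lists hypocomplementemia, and the total score is summarized only at baseline (SAP 6.2.1.2). No flare criterion changes.
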